8.2 Secondary study parameter(s)

Rates of distant metastasis free survival, overall survival and disease specific free survival and local non-salvageable recurrence free survival after 5 and 10 years are calculated by the method of Kaplan-Meier and comparisons are made by log-rank test.

8.3 Other study parameters

Characteristics of the cohort will be described in detail using mean and standard deviation for continuous variables, and count and percentage for categorical variables. To compare distribution of clinical factors among subgroups (molecular subtypes), the Chi square test are used for categorical factors and Kruskal-Wallis test for continuous factors.

8.4 Interim analysis

An analysis of futility will be performed after inclusion of 325 patients and a minimum median follow up time of 16.2 months. Assuming a 5 year follow up and a 5 year uniform accrual, assuming as well an exponential distribution for survival, we calculated that the expected number of events when 325 patients are included should be at most 6, under the null hypothesis. If less or equal events are observed at that time, the trial continues and 595 patients in total needed to achieve power of >80% (an one-side alpha of 0.5). The expected number of events during the study are 35 to exclude a local recurrence risk at 5 years of 6% or more.

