4.4 Sample size calculation

Reported 5 year local and locoregional recurrence rates for patients with stage 2 and 3 disease (cT1-4N0-3) treated with NST, breast conserving surgery and radiotherapy who achieve pCR range from 0 to 3.5%, in which patients with DCIS (all reports) and even isolated tumour cells (one report, with highest reported LR of 3.5%(23)) were included in the pCR group.

As radiotherapy in primary breast cancer reduces recurrence with at least a factor 2.5, local recurrence at 5 year without radiotherapy could be in the range of 0-8.75% for pCR patients.(28)

Recently, 5-year local recurrence rates in NST patients treated with breast conserving surgery without radiotherapy were reported in a relatively large group of 110 pCR patients, with a very low recurrence rate of 1.8%. Notably, this concerned a group of cT1-4N0-3 patients, with >60% of patients being node-positive. Also, residual DCIS was included in the pCR group.(27)

As we will include only node negative patients with tumours <5 cm AND will exclude patients with residual DCIS, we may expect the recurrence rate to be on the lower side of the hypothesized range of 0-8.75%. For our statistical analysis, we have therefore used an **expected rate of local recurrence of 4%**.

A 5 year **local recurrence rate of less than 6% is deemed acceptable**, as studies have shown that the effect of RT on local recurrence is mainly achieved in the first 5 years following treatment(40), especially in TN and Her2 positive subtypes which will constitute the majority of our population.

Simulations were performed to calculate the sample size of a two stage single arm trial (including an interim analysis of futility), using the one sample log rank test. Assuming a 5 year follow up and a 5 year uniform accrual, assuming as well an exponential distribution for survival, we calculated that the expected number of events when 325 patients are included should be at most 6, under the null hypothesis. If less or equal events are observed at that time, the trial continues and **595 patients** in total are needed to achieve a power of >80% (an one-side alpha of 0.05). The expected number of events during the study are 35 to exclude a local recurrence risk at 5 years of 6% or more, if the actual local recurrence rate is 4%.

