6.7 Premature termination of the study

If the interim analysis for futility shows a higher than acceptable local recurrence rate, the study will be terminated. See statistics for detailed information.

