8. STATISTICAL ANALYSIS

8.1 Primary study parameter(s)

The primary endpoint of the study is the local recurrence rate, defined as recurrence in the ipsilateral breast. Any LR is considered as an event and is included in the analysis. Time to LR will be estimated by the Kaplan-Meier method and compared to the acceptable rate of 6% at 5 years by the one sample log rank test. Additionally an estimation of cumulative incidence of LR using death as a competing risk will be computed.

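### The futility limit of 6 events fits the 6% null only near the planned accrual; with slower accrual it can stop the trial at an acceptable recurrence rate, and power falls

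*Protocol*

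**What the plan says.** Protocol 8.4 fixes when the look takes place: "An analysis of futility will be performed after inclusion of 325 patients and a minimum median follow up time of 16.2 months". The follow-up condition is a floor; no ceiling is given. The limit is a count: the number of events "should be at most 6, under the null hypothesis. If less or equal events are observed at that time, the trial continues". Section 4.4 gives the same limit, and both sections derive it under 5-year uniform accrual and exponential event times.

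Section 6.7 states the consequence as a rate and refers back for detail: "If the interim analysis for futility shows a higher than acceptable local recurrence rate, the study will be terminated. See statistics for detailed information". What counts as acceptable is in 4.4: a 5-year "local recurrence rate of less than 6% is deemed acceptable". The final analysis in 8.1 is already scaled to follow-up: time to local recurrence is "compared to the acceptable rate of 6% at 5 years by the one sample log rank test", a test that sets observed events against those expected for the person-time observed.

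**The concern.** A fixed count matches a fixed rate only at one amount of person-time. Faster accrual is covered, because the look must then wait for the 16.2-month median. Slower accrual is not: when patient 325 enters, the earlier patients have been followed for longer, more events are expected at any given rate, and the limit is still 6.

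Two things follow. A trial whose true rate is the assumed 4% becomes more likely to stop, so power drops below the stated 80%. And once 7 or more events are expected at 6%, the count in 8.4 can be exceeded while the estimated 5-year rate is still below 6%. Sections 6.7 and 8.4 then give different answers on whether the trial ends.

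**Working it through.** **Inputs.** From 4.4, 8.1 and 8.4: null rate 6% and expected rate 4% at 5 years; 595 patients; look at patient 325; limit 6; "an one-side alpha of 0.05" (8.4 prints 0.5 for the same design; 0.05 is used here). Assumed: total accrual time A, varied from the planned 5 years up to 8.

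**Hazards.** h0 = −ln(0.94)/5 = 0.012375 per year; h1 = −ln(0.96)/5 = 0.008164 per year.

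**Expected events at the look.** Patient 325 enters at T = (325/595) × A. Follow-up is then uniform on (0, T), with median T/2, and the expected number of events is 325 × [1 − (1 − e^(−hT))/(hT)].

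**The plan's own figures (A = 5).** T = 2.73 years; median follow-up 16.4 months (stated minimum 16.2). E0 = 5.43 events at 6%, or 5.43/0.012375 = 439 person-years; E1 = 3.60 at 4%. The limit of 6 is 5.43 rounded up. With the final one-sample log-rank test 5 years after the last patient enters, using all follow-up, 35.3 events are expected at 4% (stated 35). Simulated power is 80% with variance E and 82% with variance (O + E)/2. The design reproduces.

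**Where the count and the rate part.** E0 = 7 needs 7/0.012375 = 566 person-years. That is reached at A = 6.47 years, i.e. 595/6.47 = 92 patients a year instead of 595/5 = 119, with a median of about 21 months. The 5-year rate estimated from 7 events is 1 − exp(−5 × h0 × 7/E0).

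**Fixed limit of 6 under slower accrual** (60,000 simulated trials per cell; final test Z < −1.645 at A + 5 years):

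| Accrual A (years) | 5 | 6 | 6.5 | 7 | 8 |
|---|---|---|---|---|---|
| Median follow-up at look (months) | 16.4 | 19.7 | 21.3 | 22.9 | 26.2 |
| E0 (6%) | 5.43 | 6.50 | 7.04 | 7.57 | 8.63 |
| E1 (4%) | 3.60 | 4.31 | 4.67 | 5.02 | 5.73 |
| 5-year rate estimated from 7 events | 7.7% | 6.4% | 6.0% | 5.6% | 4.9% |
| Stop, true 4% | 7% | 14% | 19% | 24% | 35% |
| Stop with fewer events than E0, true 4% | 0% | 0.4% | 5% | 11% | 23% |
| Power, true 4% | 80% | 77% | 74% | 70% | 61% |
| Stop, true 6% | 30% | 47% | 55% | 63% | 75% |
| Type I error | 4.1% | 3.7% | 3.4% | 3.0% | 2.5% |

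**Late data cut at planned accrual.** With a cut 1, 3 or 6 months after patient 325, stopping at a true 4% is 9%, 14% or 22%, and power is 79%, 76% or 69%.

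**A limit scaled to E0.** The midpoint between 6 and 7 at planned timing gives (6.5 − 5.43)/√5.43 = 0.46. Stopping if (O − E0)/√E0 > 0.46 gives:

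| Accrual A (years) | 5 | 6 | 6.5 | 7 | 8 |
|---|---|---|---|---|---|
| Stop, true 4% | 7% | 7% | 6% | 5% | 5% |
| Power, true 4% | 80% | 82% | 84% | 85% | 87% |
| Stop, true 6% | 31% | 31% | 31% | 31% | 31% |
| Type I error | 4.1% | 4.2% | 4.2% | 4.1% | 4.3% |

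Power rises with A because slower accrual also lengthens total follow-up; without an interim look it would rise from 85% to 90%.

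**The case against.** *The design is right as stated, and no delay is reported.* True. The accrual assumption is open, and the limit of 6 tolerates modest drift: it is the scaled limit for E0 from 4.97 to 5.88, roughly 4.6 to 5.4 years of accrual. The clash with 6.7 needs accrual about 29% longer than planned. This restricts the point to slow accrual but does not remove it, since a floor without a ceiling leaves exactly that case open.

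*Section 8.4 never says that 7 events stop the trial; termination is in 6.7 and is rate-based.* The literal reading is correct. But 6.7 sends the reader to the statistics, where the count is the only criterion. A data safety committee with a statistician (7.5) could use judgement, but would have no written rule for it.

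*A late data cut departs from the wording of 8.4.* Largely fair: events are to be counted when the two conditions are met, so this route is secondary.

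*Recurrence is assessed yearly (sections 3 and 6.3), so events are seen later than simulated.* This stands as a limit on size. At the extreme where recurrences surface only at annual visits, stopping at a true 4% is about 1%, 4%, 6%, 9% and 17% for 5, 6, 6.5, 7 and 8 years. The direction is the same. The scaled rule would then stop about 8 to 15% of trials at a true 6% under 6- to 8-year accrual, against 19 to 52% for the fixed count. That is still no less often than the roughly 7% which either rule gives at the planned timing under the same extreme.

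*Erring towards stopping is defensible when radiotherapy is withheld.* It is, if chosen. Here the extra strictness would arise from recruitment speed, and the stated power would no longer hold.

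*At planned timing 6 events estimate 6.6%, above acceptable, and the trial continues.* Also true. It is a further reason for 6.7 to cite the rule instead of describing a rate.

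**Conclusion.** The concern holds. The limit of 6 events is sound at the planned accrual, where the stated power reproduces, and becomes too strict as accrual slows. At a true 4% the loss is about 4 points of power at 6-year accrual, 10 at 7 years and 19 at 8 years. From about 6.5 years the trial can stop on an estimated rate below the 6% that the protocol calls acceptable. Type I error falls, so the harm is wrongful stopping and lost power, not a false claim of safety.

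The sizes assume uniform accrual, exponential event times, prompt detection of recurrences, a look when patient 325 enters, and a final analysis using all follow-up. The delays are scenarios. Detection at annual visits would make the stopping figures smaller. The change should be made before the interim look.

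**What to change.** In 8.4 and 4.4, replace the fixed count with a limit relative to the null expectation at the actual data cut: E0 = (−ln 0.94/5) × person-years of the first 325 patients. A possible wording: *the trial stops for futility if (O − E0)/√E0 > 0.46, where O is the number of local recurrences among these patients*. Solving E0 + 0.46√E0 = k for k = 6 to 10 gives the equivalent counts:

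| E0 | Stop if events are |
|---|---|
| 4.97–5.88 (planned 5.4) | more than 6 |
| 5.88–6.80 | more than 7 |
| 6.80–7.72 | more than 8 |
| 7.72–8.65 | more than 9 |

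The value 0.46 only reproduces the present limit at the planned timing; another scaling by E0 would also serve. Section 6.7 should refer to this rule.

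The cost is one sentence each in 8.4 and 4.4 and a cross-reference in 6.7. No new data are needed: the rule uses the observed and expected events of the test already in 8.1. One consequence should be disclosed. At a late look the scaled rule stops less often at a true 6% than the fixed count would: about 31% instead of 47%, 55%, 63% and 75% at 6-, 6.5-, 7- and 8-year accrual. Type I error stays at 4.1–4.3% instead of falling to 2.5%. The sponsor and the data safety committee should accept this knowingly.

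### Section 8.4 prints the one-sided alpha as 0.5, section 4.4 prints 0.05 for the same design; only 0.05 makes 595 the number of patients needed

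*Protocol*

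**What the plan says.** Section 4.4 (Sample size calculation) describes a single-arm trial in two stages with a futility look, an acceptable 5-year local recurrence limit of 6% and an expected rate of 4%. It says that 595 patients "in total are needed to achieve a power of >80% (an one-side alpha of 0.05").

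Section 8.4 (Interim analysis) repeats this design almost sentence for sentence. The interim is described as follows: "An analysis of futility will be performed after inclusion of 325 patients and a minimum median follow up time of 16.2 months". The planning assumptions are given as "Assuming a 5 year follow up and a 5 year uniform accrual, assuming as well an exponential distribution for survival". The limit for continuing is stated as "the expected number of events when 325 patients are included should be at most 6, under the null hypothesis". The section then gives the total size: "595 patients in total needed to achieve power of >80% (an one-side alpha of 0.5"). Both sections end with 35 expected events.

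Section 8.1 (Primary study parameter) defines the test. Time to local recurrence is estimated by Kaplan-Meier and "compared to the acceptable rate of 6% at 5 years by the one sample log rank test". It gives no significance level.

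**The concern.** One design has one significance level, and the two sections differ by a factor of ten. Alpha sets the threshold at which the trial may claim that 5-year local recurrence is below 6%. Section 8 is where an analyst looks for that threshold, and 0.5 is the only value printed there. A one-sided level of 0.5 hardly tests anything: success would be declared whenever the observed count fell just below the count expected under a 6% rate. Two questions follow. Which value did the sample size use? And does the slip reach any other figure in the design?

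**Working it through.** **Inputs from the protocol.** Null 5-year rate 6% (4.4, 8.1); alternative 4% (4.4); exponential times, 5-year uniform accrual, 5-year follow-up (4.4, 8.4); 595 patients in total; interim at 325 patients with at least 16.2 months' median follow-up; stop if more than 6 events.

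**Assumptions added.** The 5-year follow-up is read as running from the end of accrual, so patients are followed for 5 to 10 years. The test statistic is Z = (O − E)/√E, rejecting when Z < −z(1−α).

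**Step 1: hazards.**
- Null: −ln(0.94)/5 = 0.012375 per year.
- Alternative: −ln(0.96)/5 = 0.008164 per year.
- Ratio: 0.660.

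**Step 2: reproduce the stated event count.** With accrual over 5 years and analysis at year 10, expected events = N × [1 − (e^(−5λ) − e^(−10λ))/(5λ)].
- Under 4%: 595 × [1 − (0.96 − 0.9216)/0.040822] = 35.3. The protocol says 35.
- Under 6%: 595 × [1 − (0.94 − 0.8836)/0.061875] = 52.7.

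**Step 3: reproduce the interim.** Accrual is 595/5 = 119 per year, so patient 325 enters at 325/119 = 2.73 years. Median follow-up is then about half of that, 16.4 months (stated 16.2). Simulated expected events under 6% are 5.4 (stated at most 6).

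Steps 2 and 3 confirm the reading of the design but do not involve alpha, so they cannot tell 0.05 from 0.5. Only the pairing of 595 patients with power just above 80% can.

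**Step 4: simulate the two-stage design at N = 595.** There were 40,000 to 100,000 simulated trials per scenario. The ranges cover simulation error and two interim timings: at the 325th inclusion, or once median follow-up also reaches 16.2 months.

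| One-sided alpha | Two-stage power at 4% | False-positive rate at 6%, two-stage | False-positive rate at 6%, final test alone |
|---|---|---|---|
| 0.05 | 0.798–0.807 | 0.041–0.043 | 0.045–0.047 |
| 0.5 | 0.921–0.928 | 0.39–0.41 | 0.51 |

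With the interim at the 325th inclusion, alpha 0.025 gives 71% power and alpha 0.1 gives 87%.

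**Step 5: ask which alpha makes 595 the number needed.**
- At 0.05, with the interim at the 325th inclusion, power is 79.1% at 580 patients, 79.8% at 590 and 80.4% at 595. It crosses 80% at about the stated size.
- At 0.5, a single-stage test would need about 45 patients for 80% power. With the interim kept and accrual at 119 per year, 330 patients already give 91.5%. Power cannot rise much above 93%, because the futility rule lets only about 93% of trials continue at a true rate of 4%.

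**Step 6: the decision rule each value implies.** Taking E at its null expectation of 52.7:
- At 0.05: 52.7 − 1.645 × √52.7 = 40.7. In simulation under 6%, trials reject always at 40 or fewer events, in about two-thirds of cases at 41, and never at 43.
- At 0.5: z = 0, so success is any count below E. In simulation, about 93% of trials reject at 52 events and almost none at 54.

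**The case against.** **Most of the matching figures do not discriminate.** The 35 events and the interim limit would be the same at any alpha, and the 92 to 93% power at 0.5 also satisfies a literal reading of above 80%. This is correct. The case for 0.05 rests on 595 being about the smallest size that reaches 80% at that level, which step 5 shows. At 0.5, 595 would not be needed.

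**The reproduction depends on how follow-up is read.** If each patient is followed for exactly 5 years, events under 4% are 595 × 0.04 = 23.8 and power at 0.05 is about 69%. Neither matches the protocol. The longer reading gives the stated 35 events, which supports it, but it remains an assumption, as does the √E variance. The conflict between 4.4 and 8.4 needs neither assumption.

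**The false-positive figures are hypothetical.** They arise only if someone tests at 0.5. Section 4.4 gives 0.05, the value in 8.4 sits in brackets inside a repeated sample-size statement, and a statistical analysis plan may restate the level. This limits the practical risk and stands as a point about weight. The absence of a level in 8.1 is not an error in itself. What remains is a wrong figure printed in the statistical section, which another document cannot make right.

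**The text alone cannot exclude a digit lost in conversion from PDF.** Nothing points to this, and a look at the protocol file settles it.

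**Conclusion.** The two sections contradict each other, and 0.5 in section 8.4 is wrong as written. The design was evidently calculated at a one-sided 0.05, which gives about 80% power at 595 patients. The sample size, stated power, futility rule and event count do not change.

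The printed level is out by a factor of ten. Used literally at a true 5-year rate of 6%, it would raise the two-stage false-positive rate from about 4% to about 40%, and that of the final test alone from about 5% to about 51%. It would move the success limit from about 40 or 41 events to anything below about 53. These sizes rest on exponential times, 5 years of follow-up after accrual closes and the √E form of the test. The slip is editorial in origin, but it concerns the threshold of the primary test and should be corrected.

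**What to change.** In section 8.4, change the one-sided alpha from 0.5 to 0.05 so that it agrees with section 4.4. Optionally, state the one-sided 0.05 level in section 8.1 as well, where the test against 6% is defined, so that section 8 can be read on its own. This is a one-figure text correction. Nothing in the design, the sample size or the conduct of the trial changes.

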9. ETHICAL CONSIDERATIONS

9.1 Regulation statement

The study will be conducted according to the principles of the Declaration of Helsinki (version 2013) and in accordance with the Medical Research Involving Human Subjects Act (WMO) and other guidelines, regulations and Acts.

9.2 Recruitment and consent

Patients eligible for the study will be contacted during the pre-operative outpatient clinical appointment by a specialist. Patients will receive oral information and a patient information letter as well as the informed consent form (see attachment). Patients will be given enough time to consider the provided information and ask questions about it. Every patient will receive a copy of the signed informed consent form. The informed consent form must be signed within 16 weeks following the date of surgery.

9.3 Objection by minors or incapacitated subjects

Not applicable.

9.4 Benefits and risks assessment, group relatedness

Patients participating in this study will be spared side-effects associated with radiotherapy. Patients in which radiotherapy is omitted may have a higher risk of developing a local recurrence. The majority of local recurrences can be treated with breast conserving therapy and radiotherapy. Extra burden during the study are additional questionnaires according quality of life which will be provided simultaneously with the PROMs, which are integrated in standard care in the Antoni van Leeuwenhoek and other centers.

9.5 Compensation for injury

The sponsor/investigator has a liability insurance which is in accordance with article 7 of the WMO.

The sponsor (also) has an insurance which is in accordance with the legal requirements in the Netherlands (Article 7 W MO). This insurance provides cover for damage to research subjects through injury or death caused by the study.

The insurance applies to the damage that becomes apparent during the study or within 4 years after the end of the study.

9.6 Incentives

Not applicable.

10. ADMINISTRATIVE ASPECTS, MONITORING AND PUBLICATION

10.1 Handling and storage of data and documents

The central data management will be performed by the Netherlands Cancer Institute-Antoni van Leeuwenhoek. Registration will be done after the written informed consent is obtained and after verification of eligibility. After the written informed consent is obtained, patients will be assigned to a registration number.

Registration will be performed using ALEA® registration package run by the NKI Data Center.

All data that are relevant for the study will be collected on eCRFs developed by the NKI data Center. The system can be accessed via internet to include data directly in the Data Centre Servers. The AVL Datacenter will supply accounts to the local data manager to enter data into the system. Checks will be incorporated into the eCRF system to prompt queries at the moment that data is entered facilitating the work of the local data manager who could quickly correct errors. Additional checks will be programmed using statistical programs with the goal of obtaining a clean file.

The time between the patient's visit and completion of eCRF pages should be kept to a reasonable minimum allowing answering the questions posed by the study. In all cases it remains the responsibility of the investigator to check and validate the data after verifying that they are completed and filled out correctly. If information is not known, this must be clearly indicated.

The investigator will retain all pertinent information for a period of at least 15 years from study completion.

